#### **7.1.2.6 Administration of Pembrolizumab (30-minute Infusion)**

Administration of pembrolizumab will be witnessed by the investigator and/or trial staff. The total volume of trial treatment infused will be compared to the total volume prepared to determine compliance with each dose administered.

The instructions for preparing and administering pembrolizumab will be provided in the Pharmacy Manual.

### **7.1.3 Laboratory Procedures/Assessments**

Details regarding specific laboratory procedures/assessments to be performed in this trial are provided below. The total amount of blood/tissue to be drawn/collected over the course of the trial (from pre-trial to post-trial visits), including approximate blood volumes drawn/collected by visit and by sample type per subject can be found in Section 12.2.

#### **7.1.3.1 Laboratory Safety Evaluations (Hematology, Chemistry, and Urinalysis)**

Laboratory tests for hematology, chemistry, and urinalysis are specified in [Table 6](#).

Table 6 Laboratory Tests

Hematology	Chemistry	Urinalysis	Other
Hematocrit	Albumin	Blood	Pregnancy test (serum or urine) a
Hemoglobin	Alkaline phosphatase	Glucose	
Platelet count	Alanine aminotransferase	Protein	PT/INR
WBC (total and differential) e	Aspartate aminotransferase	Specific gravity	aPTT
RBC	Bicarbonate c	Microscopic exam, if abnormal results are noted	Total T3 or free T3, FT4, and TSH b,d
Absolute lymphocyte count e	Calcium		Anti-HCV
Absolute neutrophil count e	Chloride		HCV viral load d
	Creatinine		HCV genotype d
	Glucose		anti-HBs d
	Phosphorus		HbsAg
	Potassium		Anti-HBc (total and IgM) d
	Sodium		HbeAg d
	Total bilirubin		anti-Hbe d
	Direct bilirubin		HBV viral load d
	Total protein		Anti-HDV d
	Blood urea nitrogen		AFP
			CRP
			GGT

a Perform on women of childbearing potential only 72 hours prior to Day 1 of Cycle 1. Pregnancy tests must be repeated prior to every cycle if required or as specified per local regulatory guidance.

b T3 is preferred; if not available free T3 may be tested.

c If this test is not done as part of local standard of care, this test does not need to be performed.

d If the local laboratory is unable to perform these tests, the site should submit the sample to the central laboratory for testing. Details are provided in the Procedure Manual.

e Report % or absolute results per standard of practice. Report the results in the same manner throughout the trial.

AFP=alpha-fetoprotein; aPTT=activated partial thrombin time; CRP=C-reactive protein; FT4=free thyroxine; GGT=gamma-glutamyl transferase; HBc=Hepatitis B core; HbeAg=Hepatitis B e antigen; Hbe=hemoglobin E; HBs=hepatitis B surface; HbsAg=hepatitis B surface antigen; HBV=hepatitis B virus; HCV=hepatitis C virus; HDV=hepatitis D virus; IgM=gamma M immunoglobulin; INR=insulin receptor; PT=prothrombin time; RBC=red blood cells; T3= triiodothyronine; TSH=thyroid-stimulating hormone (thyrotropin); WBC=white blood cells.

Laboratory tests for screening should be performed within 10 days prior to the first dose of trial treatment. An exception is hepatitis and thyroid serologies, which may be performed within 30 days prior to first dose. After Cycle 1, pre-dose laboratory safety tests can be conducted up to 72 hours prior to dosing unless otherwise noted on the flow charts.

Laboratory test results must be reviewed by the Investigator or qualified designee and found to be acceptable prior to administration of each dose of trial treatment. Unresolved abnormal laboratory values that are drug-related AEs should be followed until resolution. Laboratory

tests do not need to be repeated after the end of treatment if laboratory results are within the normal range.

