### 5.2.1.2 Dose Modification (Escalation/Titration/Other)

#### 5.2.1.2.1 Immune-Related Events and Dose Modification (Withhold, Treat, Discontinue)

##### **Dose Modification and Toxicity Management for Immune-related AEs Associated with Pembrolizumab**

AEs associated with pembrolizumab exposure may represent an immune-related response. These irAEs may occur shortly after the first dose or several months after the last dose of pembrolizumab treatment and may affect more than one body system simultaneously. Therefore, early recognition and initiation of treatment is critical to reduce complications. Based on existing clinical study data, most irAEs were reversible and could be managed with interruptions of pembrolizumab, administration of corticosteroids and/or other supportive care. For suspected irAEs, ensure adequate evaluation to confirm etiology or exclude other causes. Additional procedures or tests such as bronchoscopy, endoscopy, skin biopsy may be included as part of the evaluation. Based on the severity of irAEs, withhold or permanently discontinue pembrolizumab and administer corticosteroids.

Dose Modification and Toxicity Management Guidelines for irAEs associated with pembrolizumab monotherapy, coformulations, or IO combinations are provided in [Table 4](#).

**Table 4 Dose Modification and Toxicity Management Guidelines for Immune-related Adverse Events Associated with Pembrolizumab Monotherapy, Coformulations or IO Combinations**

General instructions:				
irAEs	Toxicity Grade (CTCAEv4.0)	Action With Pembrolizumab Monotherapy, Coformulations or IO Combinations	Corticosteroid and/or Other Therapies	Monitoring and Follow-up
Pneumonitis	Grade 2	Withhold	

Administer corticosteroids (initial dose of 1-2 mg/kg prednisone or equivalent) followed by taper

	

Monitor participants for signs and symptoms of pneumonitis

Evaluate participants with suspected pneumonitis with radiographic imaging and initiate corticosteroid treatment

Add prophylactic antibiotics for opportunistic infections

	Recurrent Grade 2 or Grade 3 or 4	Permanently discontinue		

irAEs	Toxicity Grade (CTCAEv4.0)	Action With Pembrolizumab Monotherapy, Coformulations or IO Combinations	Corticosteroid and/or Other Therapies	Monitoring and Follow-up

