## 6.0 TRIAL FLOW CHART

	Screening	Week/Cycle (21-day Cycle)									Visit 10 and Beyond (21-day Cycle)	End of Treatment (EOT)  Treatment Discontinuation	Safety Follow-up 
												At time of treatment discontinuation	(30 days after EOT or prior to start of new antineoplastic therapy)
Treatment Cycle	-30 to -1	1	2	3	4	5	6	7	8	9	10-35		
Week (approximate)		0	3	6	9	12	15	18	21	24			
Scheduling Window: Days		±3	±3	±3	±3	±3	±3	±3	±3	±3	±5	+7	+7
Administrative Procedures													
Informed Consent 	X												
Inclusion/Exclusion Criteria	X												
Subject Identification Card	X (dispense)										X (collect)		
Demographics/Medical History and Prior Medications 	X												
Review Concomitant Medications		X	X	X	X	X	X	X	X	X	X	X	X
Clinical Procedures/Assessments													
Review Adverse Events		X	X	X	X	X	X	X	X	X	X	X 	
ECOG Performance Status	X 	X 	X	X	X	X	X	X	X	X	X	X	X
Physical Examination	X	X	X	X	X	X	X	X	X	X	X	X	X
Vital Signs and Weight 	X	X	X	X	X	X	X	X	X	X	X	X	X
12-Lead ECG 	X				X				X		X 	X	X
Administration of Pembrolizumab (30-min Infusion)		X	X	X	X	X	X	X	X	X	X		

	Screening	Week/Cycle (21-day Cycle)									Visit 10 and Beyond (21-day Cycle)	End of Treatment (EOT)  Treatment Discontinuation	Safety Follow-up 
												At time of treatment discontinuation	(30 days after EOT or prior to start of new antineoplastic therapy)
Treatment Cycle	-30 to -1	1	2	3	4	5	6	7	8	9	10-35		
Week (approximate)		0	3	6	9	12	15	18	21	24			
Scheduling Window: Days		±3	±3	±3	±3	±3	±3	±3	±3	±3	±5	+7	+7
Laboratory Procedures/Assessments 													
Hepatitis B and C 	X												
Pregnancy Test- Urine or Serum β-HCG 	X	X	X	X	X	X	X	X	X	X	X		
PT/INR and aPTT 	X												X
CBC With Differential 	X		X	X	X	X	X	X	X	X	X		X
Comprehensive Serum Chemistry Panel 	X		X	X	X	X	X	X	X	X	X		X
Urinalysis 	X		X			X				X	X		X
T3, FreeT4 (FT4), and TSH 	X		X		X		X		X	X	X		X
ALK Translocation Testing, NSCLC subjects only 	X												
EGFR Mutation Testing, NSCLC subjects only 	X												
Disease Assessments													
Tumor Imaging 	X				X			X		X 	X 		
Brain Imaging 	X				X					X 	X 		

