## 8.5 Analysis Populations

### 8.5.1 Safety Analysis Populations

The All Subjects as Treated (ASaT) population will be used for the analysis of safety data in this study. The ASaT population consists of all subjects who received at least 1 dose of trial treatment.

At least 1 laboratory or vital sign measurement obtained subsequent to at least 1 dose of trial treatment is required for inclusion in the analysis of each specific parameter. To assess change from baseline, a baseline measurement is also required.

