**12.2 Approximate Blood/Tissue Volumes Drawn/Collected by Trial Visit and by Sample Types**

Screening	Cycle 1	C2	C3	C 4	C5	C6	C7	C8	C9	C10-35	EOT	Follow up
15 ml		10.5 ml	5.5 ml	5.5 ml	5.5 ml	10.5 ml	5.5 ml	5.5 ml	5.5 ml	10.5ml	10.5ml	13.5 ml

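### Section 7.1.3.1 makes post-treatment laboratory tests optional for subjects with normal results, while the flow chart schedules them for everyone, so late laboratory ascertainment may depend on earlier results

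*Combined protocol and SAP*

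**What the plan says.** Section 7.1.3.1 gives two rules side by side for laboratory values late in the trial. The first is "Unresolved abnormal laboratory values that are drug-related AEs should be followed until resolution". The second is that laboratory "tests do not need to be repeated after the end of treatment if laboratory results are within the normal range".

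The Trial Flow Chart has no such condition. Its rows for "CBC With Differential" and "Comprehensive Serum Chemistry Panel", and those for urinalysis, thyroid tests and PT/INR with aPTT, are all marked at Safety Follow-up and blank at EOT. Footnote 10 says that coagulation should be collected at Screening and at Safety Follow-up. Section 7.1.5 makes the flow chart the source of visit requirements, and Section 7.1.5.3 calls the Safety Follow-up visit mandatory. Appendix 12.2 lists 10.5 ml at EOT and 13.5 ml at Follow up.

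On analysis, Section 8.5.1 sets a rule that it applies parameter by parameter: "At least 1 laboratory or vital sign measurement obtained subsequent to at least 1 dose of trial treatment is required for inclusion". Section 5.2.1.2.1 says of immune-related events: "These irAEs may occur shortly after the first dose or several months after the last dose of pembrolizumab treatment".

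**The concern.** Safety is the trial's only objective, and Section 4.2.3.2 names changes in laboratory values among the safety endpoints. If the one scheduled post-treatment sample may be skipped because an earlier result was normal, measurement of an endpoint depends on that endpoint's own history. The skipped subjects are those in whom an abnormality would be new. An asymptomatic rise in liver enzymes, creatinine or TSH in such a subject might never be measured. The hepatic event of clinical interest in Section 7.2.3.2 is defined by laboratory values and is reportable for 30 days after treatment under that section, so it can be missed in the same way.

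Sites could also differ. One that follows the flow chart tests everyone; one that follows Section 7.1.3.1 tests a selected group. The pooled summaries would then mix two collection rules.

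**Working it through.** **1. The plan's own figures.** The only computed figures in the SAP are the seven intervals in Section 8.9.1. The Clopper-Pearson limits for x events in n subjects are the 0.025 quantile of Beta(x, n−x+1) and the 0.975 quantile of Beta(x+1, n−x). For 8/150 these give 2.3% and 10.2%, as printed. All seven rows agree to 0.1 point. This point does not depend on them.

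**2. What the flow chart schedules.** Each laboratory row has 13 cells: Screening, Cycles 1 to 9, Cycles 10–35, EOT, Safety Follow-up.

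| Row | Marked on treatment | EOT | Safety Follow-up |
|---|---|---|---|
| CBC | C2–C9, C10–35 | blank | X |
| Chemistry | C2–C9, C10–35 | blank | X |
| Urinalysis | C2, C5, C9, C10–35 | blank | X |
| T3, FT4, TSH | C2, C4, C6, C8, C9, C10–35 | blank | X |
| PT/INR, aPTT | none | blank | X |

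All five rows are also marked at Screening. Safety Follow-up is therefore the only scheduled laboratory sampling after treatment ends.

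**3. Two readings of the sentence.**
- Literal: a subject whose latest result is normal needs no test after treatment. This conflicts with the flow chart, footnote 10 and the 13.5 ml follow-up volume.
- Narrow: once the scheduled follow-up result is normal, no further repeat is needed. There is then no conflict.

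The text does not choose between them.

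**4. Consequence of the literal reading, by parameter.**
- Coagulation: the only scheduled result before follow-up is the screening one. A subject with normal screening values who is skipped has no scheduled post-dose value, however many cycles were given, and Section 8.5.1 removes that subject from the coagulation analysis.
- The other four rows: most subjects already have post-dose values from Cycle 2 onward, so what is lost is the late value. A one-dose subject with normal screening results and no Cycle 2 sample could have no post-dose value for any of them.

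**5. Illustration of size.** The documents give neither the share of subjects with normal results nor the rate of late abnormalities, so both are assumed here.
- With n tested and a true late rate of 2%, the chance of seeing at least one case is 1 − 0.98^n. With no case seen, the exact upper 95% limit is 1 − 0.025^(1/n).

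| Tested (share of 150) | P(at least one case) | Upper limit, no case seen |
|---|---|---|
| 150 (100%) | 95.2% | 2.4% |
| 112 (75%) | 89.6% | 3.2% |
| 75 (50%) | 78.0% | 4.8% |
| 38 (25%) | 53.6% | 9.3% |

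- Expected cases missed = subjects skipped × late rate among them. The low end is 38 × 0.02 = 0.76; the high end is 112 × 0.05 = 5.6.

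These figures assume that every site uses the sentence and that tested and skipped subjects share the same rate. They show scale only.

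**The case against.** The strongest reply is that nothing is waived. The sentence follows directly on the rule for following unresolved abnormal values, so its natural sense may be that repeats stop once a post-treatment result is normal. It is also permissive, the flow chart governs visit requirements, and the visit is mandatory. A site that reads the protocol as a whole would still test everyone. This stands as a possible reading, but the sentence does not say it, and a site could reasonably take it the other way.

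Several further limits also stand:
- The laboratory ECI proportion in Section 8.6.1 covers the study therapy period, which is not defined. The firmer effect is on AE and ECI capture to 30 days and on change-from-baseline summaries, which are descriptive and which Section 8.6.1 says may be provided.
- The 8.5.1 measurement rule governs individual laboratory and vital-sign parameters. AE analyses keep the full ASaT population.
- The disputed sample is at about 30 days, so restoring it would not capture events that begin months later.
- Appendix 12.2 is weak support. It is headed as approximate, names no tests and does not track the flow chart on treatment: Cycles 4 and 8 carry 5.5 ml and Cycles 2 and 6 carry 10.5 ml, although thyroid tests are marked at all four.

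A reader might also infer that the blank Cycle 1 column loses post-dose data. It does not: Section 5.2.2 puts Day 1 assessments before dosing, so a Cycle 1 sample would be pre-dose. Nor is the hepatic ECI the only laboratory measure given an interval, since Table 8 also gives 95% CIs for specific AEs and PDLCs with incidence of at least 1%.

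**Conclusion.** The point holds as an unresolved conflict with a plausible effect on data collection. Read literally, Section 7.1.3.1 lets routine late laboratory testing depend on earlier results, against a flow chart that schedules it for all. Where sites use it that way, new asymptomatic abnormalities in previously normal subjects are under-detected up to the 30-day visit, and coagulation can lose its only scheduled post-dose value. The size is unknown, because it depends on how many sites use the sentence and how many subjects have normal results.

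A reader might infer more: that late toxicity is sought only in subjects already abnormal. The documents do not support that. Sections 7.1 and 7.1.2.1 allow unscheduled or additional testing in any subject, Section 7.2.3.2 counts unscheduled results, and a subject abnormal on one test can develop a new abnormality on another.

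Nor can a count of subjects lost be derived. Taking 5% to 10% of 150 as one-dose subjects gives about 8 to 15. For all of them to lose every post-dose value, none may have a Cycle 2 sample, all must be normal and every site must skip the test. Footnote 11 allows Cycle 2 blood samples up to 48 hours before dosing, and subjects stopping for laboratory toxicity would have an abnormal result. Ratios of days of observation do not measure data lost either, since follow-up is a single visit.

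The matter should be corrected, because the conflict bears on a safety endpoint in a safety trial and the remedy is cheap.

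**What to change.** Reconcile Section 7.1.3.1 with the flow chart, either by deleting the sentence or by limiting it to further repeats after a normal Safety Follow-up result. State that all tests already marked at Safety Follow-up (CBC, chemistry, urinalysis, thyroid tests, PT/INR and aPTT) are collected for the safety endpoints in every subject regardless of earlier results.

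Separately, reconcile the 10.5 ml listed at EOT in Appendix 12.2 with the flow chart, which marks no blood test there.

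The cost is a short text change in an amendment and a local laboratory panel in subjects who would otherwise have been skipped. The follow-up tests are already scheduled. If collection is already complete, report for each laboratory parameter how many subjects had a post-treatment value, so that readers can judge the gap.

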### **7.1.3.2 Pregnancy Test**

All women who are being considered for participation in the trial, and who are not surgically sterilized or postmenopausal, must be tested for pregnancy within 72 hours of each cycle of trial treatment and 30 days post-treatment, if required or as specified per local regulatory guidance. If a urine test is positive or not evaluable, a serum test will be required. Subjects must be excluded/discontinued from the trial in the event of a positive or borderline-positive test result.

### **7.1.4 Other Procedures**

#### **7.1.4.1 Withdrawal/Discontinuation**

Subjects who discontinue treatment prior to completion of the trial should be encouraged to continue to be followed for all remaining study visits.

When a subject discontinues/withdraws from participation in the trial, all applicable activities scheduled for the EOT should be performed at the time of discontinuation. Any adverse events which are present at the time of discontinuation/withdrawal should be followed in accordance with the safety requirements outlined in Section 7.2 - Assessing and Recording Adverse Events and subjects will return to the clinic for a safety follow-up visit 30 days after EOT or prior to start of the new antineoplastic therapy, whichever occurs first.

##### **7.1.4.1.1 Lost to Follow-up**

If a subject fails to return to the clinic for a required study visit and/or if the site is unable to contact the subject, the following procedures are to be performed:

- The site must attempt to contact the subject and reschedule the missed visit. If the subject is contacted, the subject should be counseled on the importance of maintaining the protocol-specified visit schedule.
- The investigator or designee must make every effort to regain contact with the subject at each missed visit (e.g. phone calls and/or a certified letter to the subject's last known mailing address or locally equivalent methods). These contact attempts should be documented in the subject's medical record.
- Note: A subject is not considered lost to follow-up until the last scheduled visit for the individual subject. The amount of missing data for the subject will be managed via the pre-specified data handling and analysis guidelines.

##### **7.1.4.2 Subject Blinding/Unblinding**

This is an open label trial; there is no blinding for this trial.

#### **7.1.4.3 Calibration of Equipment**

The investigator or qualified designee has the responsibility to ensure that any device or instrument used for a clinical evaluation/test during a clinical trial that provides information about inclusion/exclusion criteria and/or safety or efficacy parameters shall be suitably calibrated and/or maintained to ensure that the data obtained is reliable and/or reproducible. Documentation of equipment calibration must be retained as source documentation at the trial site.

#### **7.1.4.4 Tumor and Brain Imaging**

Initial tumor imaging will be performed within 30 days prior to enrollment. Computed tomography (CT) scans are the required modality for measurable disease unless a subject has a contraindication (eg, severe contrast allergy), in which case MRI is acceptable. Premedication for contrast allergy, including steroids, is permissible. Imaging timing should follow calendar days and should not be adjusted for delays in cycle starts. Imaging should be performed 12 weeks ( $\pm 7$  days) after the first cycle of treatment and then every 9 weeks ( $\pm 7$  days), or as clinically indicated.

Brain MRI must be performed at screening, 12 weeks ( $\pm 7$  days) after the first cycle of treatment, and then every 18 weeks ( $\pm 7$  days), or as clinically indicated. For subjects for whom an MRI is contraindicated, brain CT scan is acceptable.

In subjects who discontinue trial treatment, tumor imaging should be performed at the time of treatment discontinuation ( $\pm 4$  week window). If a previous scan was obtained within 4 weeks prior to the date of discontinuation, then a scan at treatment discontinuation is not mandatory. This is the final required tumor imaging.

Participants may be permitted to continue treatment beyond confirmed RECIST 1.1-defined progression as long as investigator-assessed clinical stability is observed, and the participant is tolerating study drug following Sponsor consultation and approval.

Clinical stability is defined as the following:

- Absence of symptoms and signs (including worsening of laboratory values) indicating progression of disease
- Absence of rapid progression of disease or of progressive tumor at critical anatomical sites (e.g., cord compression) requiring urgent alternative medical intervention
- No decline in ECOG performance status
- No requirements for intensified management, including increased analgesia, radiation, or other palliative care

Detailed instructions for tumor and brain imaging are provided in the Site Imaging Manual.

#### **7.1.4.5 Tumor Biopsy/Archival Tissue Collection, NSCLC Subjects Only**

Tumor tissue, for NSCLC subjects only, for biomarker analysis from formalin fixed paraffin-embedded tumor tissue sample or newly obtained formalin fixed biopsy of a tumor lesion not previously irradiated must be provided in the form of a tissue block or unstained slides and evaluated before allocation. Biopsy of lesions on study should be limited to non-target lesions or new lesions if their pathologic etiology is ambiguous.

To perform testing for PD-L1, the laboratory (local or central) must use the PD-L1 IHC 22C3 pharmDx in strict accordance with the manufacturer's instructions, which is the only assay acceptable for this study.

For 1st line NSCLC subjects only, subjects whose tumors demonstrate PD-L1 $\geq$ 50% expression is eligible for enrollment. 2nd line treatment and beyond NSCLC subjects must demonstrate PD-L1 $\geq$ 1% expression for eligibility. A fine needle aspirate, EBUS or cytologic specimen will not be acceptable. Needle or excisional biopsies, or resected tissue is required. Newly obtained formalin fixed specimens are encouraged.

Detailed instructions for NSCLC subject tissue collection, processing and shipment are provided in the Procedures Manual. Older biopsy material or surgical specimens may be used to assess EGFR mutation status and ALK translocation status, if not already documented when the subject provides documented informed consent.

